2. SUMMARY OF KEY PROTOCOL INFORMATION

2.1. Changes to the Protocol Defined Statistical Analysis Plan

There were no changes or deviations to the originally planned statistical analysis specified in the protocol 208465/Amendment 3 (Dated: 26-Oct-2021).

[figure not shown]
2.2. Study Objective(s) and Endpoint(s)

Objectives	Endpoints
Primary	Primary

 To determine safety and tolerability of belantamab mafodotin in Chinese Participants with RRMM 	
 Adverse events (AE), i.e., number (%) of participants with DLTs, number (%) of participants with AEs
Secondary	Secondary

 To evaluate PK profile of belantamab mafodotin in Chinese Participants with RRMM To evaluate safety and tolerability of belantamab mafodotin To evaluate the clinical measures of efficacy of belantamab mafodotin To assess anti-drug antibody (ADA) formation after IV single and repeat dose administration of belantamab mafodotin Participant self-reported symptomatic adverse effects by evaluation of tolerability of belantamab mafodotin 	
 ADC, total antibody and cys-mcMMAF PK parameters following IV single and repeat dose administration during dose escalation as data permit (e.g., AUC, C_{max}, t_{max}) Changes in clinical signs and laboratory parameters, ocular findings on ophthalmic exam ORR, defined as the percentage of participants with a confirmed partial response (PR) or better (i.e., VGPR, CR and stringent complete response [sCR]), according to the International Myeloma Working Group (IMWG) Response Criteria. Incidence and titers of ADAs against belantamab mafodotin Symptomatic adverse effects and related impacts as measured by the OSDI
Exploratory	Exploratory
CCI	

Abbreviations: IV = intravenous; BCMA = B-cell maturation antigen; MMAF = monomethyl auristatin-F; ORR = overall response rate; CR = complete response; DLT = dose-limiting toxicity; VGPR = very good partial response; PR = partial response; sCR = Stringent complete response; PK = pharmacokinetics; AUC = area under the curve; C_{max} = maximum concentration; T_{max} = time to maximum; ADA = anti-drug antibody; OSDI = Ocular Surface Disease Index; CCI

CCI

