8.2.7. Visual Function Questionnaire

The impact of potential ocular toxicity on function and health-related quality-of-life will be assessed with the use of a visual function questionnaire, the OSDI. All participants will use the Self-Administered version of the questionnaire, unless their vision prevents them from being able to complete the questionnaire on their own. Participants who are not able to complete the questionnaire on their own and require assistance must use an Interviewer Administered format. If the Interviewer Administered format is being used, it must be read to the participants verbatim, and participant responses must be recorded directly without any interpretation. For any additional assessments conducted via telephone (either during participation in the treatment period or during Follow-up), the Interviewer Administered format must be used.

The OSDI will be administered to participants in different regions based on the availability of translated versions.

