8.3.9. Ocular Examinations and Procedures

Participants will be assessed by ophthalmologist (or an optometrist if an ophthalmologist is not available) at screening/baseline.

A full *screening/baseline* ophthalmic examination for all participants must include for both eyes (OU):

- a. Best corrected visual acuity
- b. Documentation of manifest refraction and the method used to obtain best corrected visual acuity
- c. Current glasses prescription (if applicable)
- d. Intraocular pressure measurement
- e. Full anterior segment (slit lamp) examination including fluorescein staining of the cornea. Anterior segment exam includes: conjunctiva, sclera, cornea, lens and anterior vitreous
- f. Dilated funduscopic exam

The *on treatment* and *follow-up* ophthalmic exam should be performed for both eyes (OU) as described below and in the SoA (Section 1.3):

- 1. Best corrected visual acuity
- 2. Documentation of manifest refraction and the method used to obtain best corrected visual acuity.
- 3. Intraocular pressure measurement (if clinically indicated).
- 4. Anterior segment examination of the: conjunctiva, sclera, cornea (including fluorescein staining) and lens

The end of study treatment and last follow-up ophthalmic exam, if required, should match the screening/baseline exam.

Additional examinations should be performed at the discretion of the treating eye specialist.

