9.4.3. Safety Analyses

The All Treated Population will be used for the analysis of safety data (except the DLT analysis). All serially collected safety endpoints will be summarized according to the scheduled, nominal visit at which they were collected and across all on-treatment time points using a "worst-case" analysis. Complete details of the safety analyses will be provided in the Reporting and Analysis Plan (RAP).

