8.8. Other Safety Analyses

The analyses of non-laboratory safety test results including ECGs, ECHOs, Ocular findings and vital signs will be based on GSK Core Data Standards, unless otherwise specified. The details of the planned displays are presented in [Appendix 12: List of Data Displays](#).

Unless otherwise specified, the denominator in percentage calculation at each scheduled visit will be based on the number of participants with non-missing value at each particular visit.

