8.8.1. Performance Status

A ECOG performance status listing will also be provided.

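### OSDI, the sole endpoint of a secondary objective, has no analysis or display in the SAP; ophthalmic exam findings are promised in SAP 8.8 but have no specification and no display

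*SAP*

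**What the plan says.** SAP 2.2 gives participant-reported tolerability its own secondary objective with one endpoint, "Symptomatic adverse effects and related impacts as measured by the OSDI". A separate secondary safety objective has the composite endpoint "Changes in clinical signs and laboratory parameters, ocular findings on ophthalmic exam".

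The data for both are collected. Protocol 8.2.7 states: "The impact of potential ocular toxicity on function and health-related quality-of-life will be assessed with the use of a visual function questionnaire, the OSDI". The Schedule of Activities places OSDI at screening, Cycle 1 Day 1, every 3 weeks, end of treatment and PD follow-up. Protocol 8.3.9 requires best corrected visual acuity and, at baseline, "Full anterior segment (slit lamp) examination including fluorescein staining of the cornea", with a shorter set of procedures on treatment.

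On analysis, Protocol 9.4.3 says "All serially collected safety endpoints will be summarized according to the scheduled, nominal visit at which they were collected", adds a worst-case summary across on-treatment time points, and leaves the details to the analysis plan. SAP 8.8 says "The analyses of non-laboratory safety test results including ECGs, ECHOs, Ocular findings and vital signs will be based on GSK Core Data Standards" and refers to Appendix 12 for the displays. SAP 2.1 declares: "There were no changes or deviations to the originally planned statistical analysis specified in the protocol".

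**The concern.** Corneal toxicity is the most frequent toxicity that the protocol reports for this drug (Protocol 2.3.2). The protocol's amendment history shows that OSDI was added in Amendment 1, after the Chinese regulator asked for attention to corneal examination and patient-reported symptoms. If the SAP and its display list are followed exactly, the secondary objective that rests on OSDI goes unanswered, and the exam component of another secondary endpoint appears in no listed output.

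The comparison with earlier data also suffers. For 2.5 mg/kg in the global phase II study, Protocol 2.3.2 reports exam-based results: acuity worse than 20/50 in the better-seeing eye in 18%, 20/200 or worse in 1%, and a median of 36 days to Grade 2 or higher corneal findings. No planned display tabulates acuity or exam findings for the Chinese participants to set beside these. With up to 6 evaluable participants per cohort, by-participant listings carry most of the information, and none is planned for either kind of data.

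**Working it through.** No sample size, power or error-rate figure bears on this point. The check traces each endpoint from SAP 2.2 through SAP Sections 7 to 9 and every display list in Appendix 12.

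1. **OSDI.** In the SAP it occurs only in the endpoint table (2.2), the copied schedule (Appendix 2) and the abbreviations (Appendix 11). Protocol 9.4 does not name it, but OSDI sits under Protocol 8.2 (Safety Assessments), so the general rule in 9.4.3 reaches it.
2. **Exam findings.** SAP 8.8 names them in one general sentence. Its only subsections are 8.8.1, which says "A ECOG performance status listing will also be provided", and 8.8.2 on ECG. Two other items in that sentence do have displays: ECG has tables 4.200 and 4.210, and vital signs have listing 30.060. The fallback to standard outputs in Appendix 8 (14.8.2) covers ECG and vital signs only.
3. **Corneal adverse events.** These have tables 4.070 (preferred term and maximum grade), 4.100 (onset and duration of first occurrence), 4.110 (characteristics, including action taken) and 4.130 (dose modification), and listing 1.200.

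| Item | Analysis sentences | Tables | Figures | Listings |
|---|---|---|---|---|
| OSDI | 0 | 0 | 0 | 0 |
| Ophthalmic exam findings | 1 (SAP 8.8, general) | 0 | 0 | 0 |
| Corneal adverse events | SAP 8.3 | 4 | 0 | 1 |

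4. **Could redaction hide a row?** Safety tables run from 4.010 to 4.210 in steps of 0.010: (4.210 − 4.010)/0.010 + 1 = 21, and all 21 are visible. ICH listings run from 1.010 to 1.320: (1.320 − 1.010)/0.010 + 1 = 32, plus the extra 1.221 makes 33, again without a gap. SAP 14.12.11 states that there are no safety figures. The redactions fall after efficacy table 2.020, after table 5.010 (Immunogenicity/Biomarker), in the biomarker displays of 14.12.18 and 14.12.19, and in one non-ICH slot, 30.080. That slot follows the anti-drug antibody listing 30.070. SAP Section 9 promises a biomarker listing, which would fit it. The term OSDI is left visible elsewhere in the SAP.

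**The case against.** The best reply is that SAP 8.8 does commit to analysing ocular findings, and that absence from Appendix 12 does not cancel SAP text. The list omits other promised items too: the exposure bar graph (SAP 6.5), the Kaplan-Meier curves (7.2), the concentration-QTc plots (11.2) and any ECHO display. This stands to the extent that the defect for exam findings is a promise without specification or display. It does nothing for OSDI.

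Stronger readings are tempting, but the documents do not support them:

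- A reader might count two secondary endpoints without output. Exam findings are one component of a composite endpoint whose laboratory part has tables 4.170 to 4.190. The count is one endpoint and one component of another.
- A reader might infer that ocular tolerability goes unreported apart from event names. The corneal event outputs also give grade, onset, duration, seriousness, recurrence and action taken. Grading uses Protocol Table 7, which concerns changes in vision (its grade text is redacted).
- A reader might take the rates in Protocol 2.3.2 (keratopathy 71%, blurred vision 22%, dry eye 13%) as proof that adverse event terms cannot separate exam findings from symptoms. Those rates are themselves adverse event rates and show such a separation.
- A reader might assume an eye exam every cycle throughout. After the sixth dose, exams may drop to every 3 months if there are no Grade 2 or higher symptoms or vision changes.
- A reader might see SAP 2.1 as concealing a change. Protocol 9.4 names no OSDI analysis, and 9.4.8 names only vital signs, ECGs and ECHOs. Under the general rule in 9.4.3 this is better described as a detail left unfilled than as an undeclared change.

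**Conclusion.** The point holds in this form: OSDI has no analysis and no display, and ophthalmic exam findings have a general promise but neither specification nor display. Every ocular output visible in Appendix 12 derives from adverse events, which falls short of the by-visit and worst-case summaries in Protocol 9.4.3. The plan should be amended, because a stated secondary objective would otherwise go unanswered.

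The conclusion rests on two assumptions. First, slot 30.080 and the other redacted rows are not ocular displays. This is likely from the numbering and from SAP Section 9, but not certain. Second, the sponsor's data standards and the separately held mock shells, which are not part of the documents, do not add displays missing from Appendix 12. Even if they did, the SAP text would still lack an OSDI scoring and summary rule.

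**What to change.** Add the following to SAP 8.8 and Appendix 12, for the All Treated population by dose level:

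1. **OSDI.** State the instrument's standard scoring and its missing-item rule. Summarise the total score, observed and change from baseline, by visit. Add the worst post-baseline change, including unscheduled and telephone assessments, and a by-participant listing. The unscheduled assessments matter because extra OSDI assessments may follow visual worsening (Schedule of Activities, footnote 37), while SAP 14.5.2 keeps unscheduled visits out of by-visit tables. Flag the mode of administration, since telephone assessments must use the interviewer format (Protocol 8.2.7).
2. **Ophthalmic exam.** Give a simple summary of worst post-baseline against baseline for best corrected visual acuity and corneal exam findings, per eye or for the worse eye as pre-stated, with a by-participant listing.

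The cost is about two tables and two listings from data already collected, with no new assessments. If the sponsor decides against either set, SAP 2.1 should say so and give the reason.

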2.3. Study Design

Overview of Study Design and Key Features	
	

Note: De-escalation to 1.9 mg/kg will be allowed in case of ≥ 2 DLT at dose 2.5 mg/kg As per current available safety and efficacy information of belantamab mafodotin studies, the 3.4 mg/kg dose cohort is converted to an optional cohort in the dose-escalation study design. Escalation may not proceed if not supported by emerging clinical data from other belantamab mafodotin studies.
	
Design Features	
 Phase I, open-label dose-escalation study to explore safety, PK, tolerability, immunogenicity and clinical activity of belantamab mafodotin monotherapy in Chinese participants with RRMM. The study will enroll up to 12 evaluable participants. This study will include two dose cohorts. Up to six evaluable participants are expected for each cohort and the actual numbers will depend on the safety observed. Each participant will be involved in the study until participant have progressed, died, withdrawn consent, discontinued treatment due to other reasons, or have been lost to follow-up. Based on the 3+3 dose escalation design the anticipated size will be up to 6 evaluable participants for each dose level.
Dosing	
 Belantamab mafodotin will be administered via 30-60 min intravenous (IV) infusion once every three weeks (21 days = 1 cycle).
Time & Events	
 Refer to Appendix 2: Schedule of Activities
Treatment Assignment	
 Projected dose levels are 2.5 mg/kg and 3.4 mg/kg. De-escalation to 1.9 mg/kg will be allowed in case of ≥ 2 DLT at dose 2.5 mg/kg. The first 3 participants in 2.5 mg/kg dose group will receive the study treatment sequentially with an observation window of 7 days, to observe acute toxicities.
Interim Analysis	
 No interim analysis is planned.

2.4. Statistical Hypotheses / Statistical Analyses

Due to limited sample size and the purpose of the study, no formal statistical hypotheses are being tested. Primary objective of the study is to determine safety and tolerability of belantamab mafodotin in Chinese Participants with RRMM. Analysis of the data will only utilise descriptive methods.

3. PLANNED ANALYSES

3.1. Interim Analyses

No interim analysis is planned in this study.

3.2. Final Analyses

The final planned primary analyses will be performed after the completion of the following sequential steps:

1. All participants have completed the study as defined in the protocol, i.e., when all participants have progressed, died, withdrawn consent, discontinued treatment due to other reasons, or have been lost to follow-up.
2. All required database cleaning activities have been completed and final database release (DBR) and database freeze (DBF) has been declared by Data Management.

4. ANALYSIS POPULATIONS

Population	Definition / Criteria	Analyses Evaluated
Screened	
 • All participants who were screened for eligibility 	
 • Study Population
Enrolled	
 • All participants who passed screening and entered the study. • Note screening failures (who never passed screening even if rescreened) and participants screened but never enrolled into the study (Reserve, Not Used) are excluded from the Enrolled population as they did not enter the study. 	
 • Study Population
All Treated	
 • All eligible participants who receive at least 1 dose of study treatment. An incorrect treatment schedule or drug administration or an early termination of treatment will not result in exclusion of participants from this population. 	
 • Study Population • Safety (except the DLT analysis) • Efficacy
DLT Evaluable	
 • All the eligible participants who have received the 1st dose as planned, and experienced a DLT during the cycle 1 or completed the cycle 1. Participants who have been replaced during cycle 1 will be excluded from the DLT evaluable population. 	
 • Summary of DLT
Pharmacokinetic (PK)	
 • All participants in the "All Treated" population from whom at least one PK sample was obtained, analyzed, and was measurable. 	
 • PK

Refer to [Appendix 12](#): List of Data Displays which details the population used for each display.

4.1. Protocol Deviations

Important protocol deviations (including deviations related to study inclusion/exclusion criteria, conduct of the trial, patient management or patient assessment) will be summarised and listed.

Protocol deviations will be tracked by the study team throughout the conduct of the study in accordance with the Protocol Deviation Management Plan (PDMP) 4.0_04Jun2021.

- Data will be reviewed prior to freezing the database to ensure all important deviations are captured and categorised on the protocol deviations dataset.

- This dataset will be the basis for the summaries and listings of protocol deviations.

A listing of all inclusion/exclusion criteria deviations will also be provided.

5. CONSIDERATIONS FOR DATA ANALYSES AND DATA HANDLING CONVENTIONS

5.1. Study Treatment & Sub-group Display Descriptors

There are no treatment comparisons. Analysis of the data obtained will only utilise descriptive methods.

5.2. Baseline Definitions

For all endpoints (except as noted in baseline definitions) the baseline value will be the latest pre-dose assessment with a non-missing value, including those from unscheduled visits. If time is not collected, Day 1 assessments are assumed to be taken prior to first dose and used as baseline. For ECG analyses, participant level baseline is defined as the mean of triplicate baseline assessments.

Unless otherwise stated, if baseline data is missing no derivation will be performed and baseline will be set to missing.

Definition	Reporting Details
Change from Baseline	= Post-baseline Value – Baseline
% Change from Baseline	= $100 \times [(Post\text{-}baseline\ Value\ -\ Baseline) / Baseline]$

5.3. Other Considerations for Data Analyses and Data Handling Conventions

Other considerations for data analyses and data handling conventions are outlined in the appendices:

Section	Component
Section 14.3	Appendix 3: Assessment Windows
Section 14.4	Appendix 4: Study Phases and Treatment Emergent Adverse Events
Section 14.5	Appendix 5: Data Display Standards & Handling Conventions
Section 14.6	Appendix 6: Derived and Transformed Data
Section 14.7	Appendix 7: Reporting Standards for Missing Data
Section 14.8	Appendix 8: Values of Potential Clinical Importance

6. STUDY POPULATION ANALYSES

6.1. Overview of Planned Study Population Analyses

The study population analyses will be based on the “All Treated” population, unless otherwise specified. The summary of screening failures and reasons for screening failure will be based on the “Screened” population, unless otherwise specified.

Study population analyses including analyses of participant’s disposition, protocol deviations, demographic and baseline characteristics, prior and concomitant medications will be based on GSK Core Data Standards. Details of the planned displays are presented in [Appendix 12: List of Data Displays](#).

6.2. Participant’s Disposition

A summary of the number of participants in each of the analysis populations described in [Section 4](#) will be provided using “Screened” population.

A summary of participant status and reason for study withdrawal will be provided. This display will show the number and percentage of participants who withdrew from the study, including the primary reasons for study withdrawal. Reasons for study withdrawal will be presented in the order they are displayed in the eCRF.

A summary of study treatment status will be provided. This display will show the number and percentage of participants who are ongoing or discontinued study treatment and a summary of the primary reasons for discontinuation of study treatment. Reasons for study treatment discontinuation will be presented in the order they are displayed in the eCRF. A listing of study treatment discontinuation will be generated. The listing will include last dose date, and reasons for study treatment discontinuation.

6.3. Demographic and Baseline Characteristics

The demographic characteristics (e.g., age, race, ethnicity, sex, baseline height, baseline body weight, and baseline BMI) will be summarized and listed. Age, height, weight and BMI will be summarized using mean, standard deviation, median, minimum, and maximum. The count and percentage will be computed for sex and ethnicity.

Disease history and characteristics (e.g. time since initial diagnosis in years, stage at initial diagnosis, date of initial diagnosis) at initial diagnosis and screening will be listed. Summaries of disease characteristics at initial diagnosis and screening will be provided. Disease characteristics at screening, including stage, type of multiple myeloma, myeloma light chain, and immunoglobulin, and whether or not have extramedullary disease and lytic bone lesions will be summarized and listed.

Genetic characteristics and Cytogenetic risk for multiple myeloma participants at screening will be summarized. Genetic characteristics will be listed. A participant is considered as having high cytogenetic risk if the participant has any of the following cytogenetics: t(4;14), del17p, t(14;16).

Current medical conditions, such as liver disease medical conditions, cardiovascular risk factors and other medical conditions will be summarized and will be sorted by decreasing overall frequency. A by-participant listing of medical conditions will also be provided.

Prior anti-cancer therapy will be listed.

Prior anti-cancer therapy for multiple myeloma participants will also be summarized by type of therapy, and drug class. A summary of multiple myeloma participants' refractory to prior anti-cancer therapy by drug class will be provided.

6.4. Treatment Compliance

Summaries of study treatment exposure and dose modifications (e.g., number of dose reductions, number of dose delays) will further characterize compliance. These analyses are described in Section 6.5 'Extent of Exposure'.

